9.1.6 ECG

See Section 7.1.3 (Cardiac precaution) Section 7.5.4 (Dose modification for prolonged QTc) for guidelines on the required close monitoring of patients’ serum biochemistry values (in particular, potassium and magnesium) and the requirement for rapid correction of low values).

A screening 12-lead ECG will be performed to assess study eligibility. Additional 12-lead ECGs will be performed at a minimum at scheduled time points as indicated in Section 8. For all patients, a 12-lead ECG must be performed on cycle 1 day 1 prior to the first administration of

study drugs or within 24 hours prior to that day. This is necessary to get an accurate baseline QTcF calculation.

Table 9-1 Cardiac assessment monitoring schedule

Cycle	Day of cycle	ECG monitoring ^a
	Screening ^b	Single ECG to assess eligibility
Cycle 1	1, 5	Pre-dose: Single 12 lead ECG
	1, 5	3 hours post dose: Single 12 lead ECG
Cycle 2	1	Pre-dose: Single 12 lead ECG

^a Refer to [Table 6-7](#) for the recommended dose modifications due to QTc interval prolongation
^b The screening ECGs will be analyzed locally to assess eligibility of the patient. (Note: the mean QTc interval at baseline must be ≤ 470 msec for the patient to be eligible for participation in the trial)
 Note: If no significant QTcF prolongation is noted during the first 4 cycles, the QTc monitoring is no longer required and may be performed at the Investigator's discretion, if medically indicated.

9.1.6.1 Performance status

Performance status will be assessed according to the ECOG Performance Status Scale:

SCORE	DESCRIPTION
0	Fully active, able to carry on all pre-disease performance without restriction.
1	Restricted in physically strenuous activity but ambulatory and able to carry out work of a light or sedentary nature, e.g., light house work, office work.
2	Ambulatory and capable of all self-care but unable to carry out any work activities. Up and about more than 50% of waking hours.
3	Capable of only limited self-care, confined to bed or chair more than 50% of waking hours.

4	Completely disabled. Cannot carry on any self-care. Totally confined to bed or chair.
5	Dead.

9.1.6.2 Special tests

No special tests will be obtained. Routine standard myeloma tests will be obtained as outlined in Section 8.

9.2 Drug levels and pharmacokinetic assessments

No pharmacokinetic studies are planned.

10 Safety monitoring

10.1 Novartis Instructions for rapid notification of serious adverse events

To ensure patient safety, every SAE, regardless of suspected causality, occurring after the patient has provided informed consent and until at least 30 days after the patient has stopped study treatment must be reported to Novartis within 24 hours of learning of its occurrence.

Any SAEs experienced after this 30 days period should only be reported to Novartis if the investigator suspects a causal relationship to the study treatment. Recurrent episodes, complications, or progression of the initial SAE must be reported as follow-up to the original episode within 24 hours of the investigator receiving the follow-up information. An SAE occurring at a different time interval or otherwise considered completely unrelated to a previously reported one should be reported separately as a new event.

Information about all SAEs is collected and recorded on the Serious Adverse Event Report Form as outlined per contractual agreement; all applicable sections of the form must be completed in order to provide a clinically thorough report. The investigator must assess and record the relationship of each SAE to each specific study treatment (if there is more than one study treatment), complete the SAE Report Form in English, and send the completed, signed form by fax within 24 hours to the oncology Novartis Drug Safety and Epidemiology (DS&E) department.

The telephone and telefax number of the contact persons in the local department of Drug Safety and Epidemiology (DS&E) are included in the contractual agreement. The original copy of the SAE Report Form and the fax confirmation sheet should be kept with the case report form documentation at the study site.

Follow-up information is sent to the same contact(s) to whom the original SAE Report Form was sent, using a new SAE Report Form stating that this is a follow-up to the previously reported SAE and giving the date of the original report. Each re-occurrence, complication, or progression of the original event should be reported as a follow-up to that event regardless of when it occurs. The follow-up information should describe whether the event has resolved or

continues, if and how it was treated, whether the blind was broken or not, and whether the patient continued or withdrew from study participation.

If the SAE is not previously documented in the Investigator's Brochure or Package Insert (new occurrence) and is thought to be related to the Novartis study treatment, an oncology Novartis Drug Safety and Epidemiology (DS&E) department associate may urgently require further information from the investigator for Health Authority reporting. Novartis may need to issue an Investigator Notification (IN), to inform all investigators involved in any study with the same drug that this SAE has been reported. Suspected Unexpected Serious Adverse Reactions (SUSARs) will be collected and reported to the competent authorities and relevant ethics committees in accordance with Directive 2001/20/EC or as per national regulatory requirements in participating countries.

10.2 Millennium Instructions for rapid notification of serious adverse events

All serious adverse events (SAEs) (regardless of expectedness or causality) must be reported to Millennium Pharmacovigilance (or designee). See also Novartis Instructions for rapid notification of serious adverse events for the reporting of SAEs.

The sponsor-investigator is responsible to meet all regulations and requirements applicable to the sponsor-investigator.

Adverse events (AEs) may be spontaneously reported by the patient and/or in response to an open question from study personnel or revealed by observation, physical examination, or other diagnostic procedures must be reported to Millennium Pharmacovigilance (or designee). Any clinically relevant deterioration in laboratory assessments or other clinical finding is considered an AE. When possible, signs and symptoms indicating a common underlying pathology should be noted as 1 comprehensive event. For serious AEs, the investigator must determine both the intensity of the event and the relationship of the event to study drug administration. For serious pretreatment events, the investigator must determine both the intensity of the event and the relationship of the event to study procedures.

This is an investigator-initiated study. The principal investigator, [name] (who may also sometimes be referred to as the sponsor-investigator), is conducting the study and acting as the sponsor. Therefore, the legal/ethical obligations of the principal investigator include both those of a sponsor and those of an investigator.

Regardless of causality, SAEs and serious pretreatment events (as defined in Section 10.7) must be reported by the sponsor- to the Millennium Pharmacovigilance or designee by faxing the SAE Report using the US FDA MedWatch 3500A Form :

Fatal and Life Threatening SAEs within 24 hours but no later than 4 calendar days of the sponsor-investigator's observation or awareness of the event

All other serious (non-fatal/non life threatening) events within 4 calendar days of the sponsor-investigator's observation or awareness of the event

The SAE report must include at minimum:

- **Event term(s)**

- **Serious criteria**
- **Intensity of the event(s):** Sponsor-investigator's or sub-investigator's determination. Intensity for each SAE, including any lab abnormalities, will be determined by using the NCI CTCAE version 4.0 specified in the protocol, as a guideline, whenever possible. The criteria are available online at <http://ctep.cancer.gov/reporting/ctc.html>.
- **Causality of the event(s):** Sponsor-investigator's or sub-investigator's determination of the relationship of the event(s) to study drug administration.

In the event that this is a multisite study, the sponsor-investigator is responsible to ensure that the SAE reports are sent to Millennium Pharmacovigilance or designee from all sites participating in the study. Sub-investigators must report all SAEs to the sponsor-investigator so that the sponsor-investigator can meet his/her foregoing reporting obligations to Millennium Pharmacovigilance. Millennium Pharmacovigilance (or designee) may request follow-up information to a reported SAE or serious pretreatment event, which the sponsor-investigator will be responsible for providing to Millennium Pharmacovigilance or designee.

Millennium will provide a sample SAE Report Form representative of the information Millennium Pharmacovigilance may request in follow-up.

Planned hospital admissions or surgical procedures for an illness or disease that existed before the patient was enrolled in the study are not to be considered AEs unless the condition deteriorated in an unexpected manner during the study (e.g., surgery was performed earlier or later than planned).

For both serious and nonserious AEs, the investigator must determine both the intensity of the event and the relationship of the event to study drug administration. For serious pretreatment events, the investigator must determine both the intensity of the event and the relationship of the event to study procedures.

Intensity for each AE, including any lab abnormality, will be determined by using the NCI CTCAE, version 4.0 as a guideline, whenever possible. The criteria are available online at <http://ctep.cancer.gov/reporting/ctc.html>

Relationship to study drug administration will be determined by the investigator or sub-investigator by responding yes or no to the question: Is there a reasonable possibility that the AE is associated with the study drug(s)?

10.4 Millennium Rules for Monitoring of Adverse Events and Period of Observation

AEs, both nonserious and serious, will be monitored throughout the study as follows:

- AEs will be reported from the first dose of MLN9708 through 30 days after administration of the last dose of MLN9708. In addition, skeletal-related events that occur during the follow-up periods must be reported from the first dose of MLN9708 through death or termination of the study by the sponsor-investigator or Millennium.
- Serious pretreatment events will be reported to Millennium Pharmacovigilance or designee from the time of the signing of the informed consent form (ICF) up to first dose of MLN9708.
- Related and unrelated SAEs will be reported to Millennium Pharmacovigilance or designee from the first dose of MLN9708 through 30 days after administration of the last dose of MLN9708. All SAEs should be monitored until they are resolved or are clearly determined to be due to a patient's stable or chronic condition or intercurrent illness(es). In addition, new primary malignancies that occur during the treatment or follow-up periods must be reported, regardless of causality to study regime. All new cases of primary malignancy must be reported to Millennium Pharmacovigilance (or designee). Follow up for detection of second primary malignancies beyond the planned study is not required; however, if the sponsor-investigator learns about the occurrence of a second primary malignancy in one of the study subjects within 3 years after the last study drug administration he must report the event to Millennium Pharmacovigilance (or designee).

10.5 Procedures for Reporting Drug Exposure during Pregnancy and Birth Events

Pregnancies and suspected pregnancies (including a positive pregnancy test regardless of age or disease state) of a female subject occurring while the subject is participating in this study, or within 28 days of the subject's last dose of MLN9708, are considered immediately reportable events. Study drug(s) is to be discontinued immediately. Millennium or designee must also be contacted immediately by faxing a completed Pregnancy Form to the Millennium Department of Pharmacovigilance. The pregnancy must be followed for the final pregnancy outcome. The pregnancy, suspected pregnancy, or positive pregnancy test must be reported to MPI/PPD Drug Safety immediately by facsimile, or other appropriate method, using the Pregnancy Initial Report Form, or approved equivalent form.

The female subject should be referred to an obstetrician-gynecologist, preferably one experienced in reproductive toxicity for further evaluation and counseling.

The Sponsor-Investigator will follow the female subject until completion of the pregnancy, and must notify MPI/PPD Drug Safety immediately about the outcome of the pregnancy (either normal or abnormal outcome) using the Pregnancy Follow-up Report Form, or approved equivalent form.

If the outcome of the pregnancy was abnormal (e.g., spontaneous or therapeutic abortion), the Sponsor-Investigator should report the abnormal outcome as an AE. If the abnormal outcome meets any of the serious criteria, it must be reported as an SAE to MPI/PPD Drug Safety immediately by facsimile, or other appropriate method, as soon as possible but no later than 5 calendar days of the Sponsor-Investigator's knowledge of the event using the SAE Report Form, or approved equivalent form.

All neonatal deaths that occur within 28 days of birth should be reported, without regard to causality, as SAEs. In addition, any infant death after 28 days that the Sponsor-Investigator suspects is related to the in utero exposure to the IP should also be reported to MPI/PPD Drug Safety immediately by facsimile, or other appropriate method, as soon as possible but no later than 5 calendar days of the Sponsor-Investigator's knowledge of the event using the SAE Report Form, or approved equivalent form.

Male Subjects

If a female partner of a male subject taking investigational product becomes pregnant, the male subject taking study drug must notify the Sponsor-Investigator, and the pregnant female partner should be advised to call their healthcare provider immediately. Millennium or designee must also be contacted immediately by faxing a completed Pregnancy Form to the Millennium Department of Pharmacovigilance. Every effort should be made to follow the pregnancy for the final pregnancy outcome.

10.6 Millennium Product Complaints

A product complaint is a verbal, written, or electronic expression that implies dissatisfaction regarding the identity, strength, purity, quality, or stability of a drug product. Individuals who identify a potential product complaint situation should immediately contact MedComm Solutions (see below) and report the event. Whenever possible, the associated product should be maintained in accordance with the label instructions pending further guidance from a Millennium Quality representative.

For Product Complaints, call MedComm Solutions at [contact] ([name]) (US and International)

--

Product complaints in and of themselves are not AEs. If a product complaint results in an SAE, an SAE form should be completed and sent to PPD (refer to Section 8.2).

10.7 Serious Adverse Events

Serious adverse event (SAE) is defined as one of the following:

- Is fatal or life-threatening
 - Results in persistent or significant disability/incapacity
 - Constitutes a congenital anomaly/birth defect
 - Is medically significant, i.e., defined as an event that jeopardizes the patient or may require medical or surgical intervention to prevent one of the outcomes listed above
 - Requires inpatient hospitalization or prolongation of existing hospitalization,
 - Note that hospitalizations for the following reasons should not be reported as serious adverse events:
 - Routine treatment or monitoring of the studied indication, not associated with any deterioration in condition
 - Elective or pre-planned treatment for a pre-existing condition that is unrelated to the indication under study and has not worsened since signing the informed consent
 - Social reasons and respite care in the absence of any deterioration in the patient's general condition
- Note that treatment on an emergency outpatient basis that does not result in hospital admission and involves an event not fulfilling any of the definitions of a SAE given above is not a serious adverse event

10.8 Pregnancies

To ensure patient safety, each pregnancy occurring while the patient is on study treatment must be reported to Novartis (and Millennium, see under 10.5) within 24 hours of learning of its occurrence. The pregnancy should be followed up to determine outcome, including spontaneous

or voluntary termination, details of the birth, and the presence or absence of any birth defects, congenital abnormalities, or maternal and/or newborn complications.

Pregnancy should be recorded on a Clinical Trial Pregnancy Form and reported by the investigator to the oncology Novartis Drug Safety and Epidemiology Department (DS&E). Pregnancy follow-up should be recorded on the same form and should include an assessment of the possible relationship to the panobinostat any pregnancy outcome. Any SAE experienced during pregnancy must be reported on the SAE Report Form. Pregnancy outcomes must be collected for the female partners of any males who took study treatment in this study. Consent to report information regarding these pregnancy outcomes should be obtained from the mother.

11 Protocol amendments, or changes in study conduct

Any change or addition (excluding administrative) to this protocol requires a written protocol amendment that must be reviewed by Novartis, Millennium, and the sponsor-investigator before implementation. Amendments significantly affecting the safety of subjects, the scope of the investigation or the scientific quality of the study require additional approval by the IRB at each study center. A copy of the written approval of the IRB must be provided to Novartis and Millennium. Examples of amendments requiring such approval are:

1. increases in drug dose or duration of exposure of subjects,
2. significant changes in the study design (e.g. addition or deletion of a control group),
3. increases in the number of invasive procedures,
4. addition or deletions of a test procedure required for monitoring of safety.

These requirements for approval should in no way prevent any immediate action from being taken by the investigator or by Novartis in the interests of preserving the safety of all patients included in the trial. If an immediate change to the protocol is felt to be necessary by the investigator and is implemented for safety reasons Novartis must be notified and the IRB at the center must be informed immediately. Amendments affecting only administrative aspects of the study do not require formal protocol amendments or IRB approval but the IRB must be kept informed of such administrative changes. Examples of administrative changes not requiring formal protocol amendments and IRB approval include:

1. changes in the staff used to monitor trials
2. minor changes in the packaging or labeling of study drug.

Any departures from the protocol must be fully documented in the source documents.

12 Data review and management

12.1 Data Management

12.2 Analyses and Reporting

Oncore will be used for data entry and analysis. Data will be analyzed and reported in abstract form after the last patient has completed the first cycle and a full manuscript will be submitted once the last patient has gone off this up to 6 month duration study. In addition, interim

reports may be submitted as abstracts. Data Safety Monitoring Plan This protocol will adhere to the policies of the Case Comprehensive Cancer Center Data and Safety Monitoring Plan in accordance with NCI regulations.

12.3 Study Monitoring

Internal monitoring by quality control teams of the Cleveland Clinic Taussig Cancer Institute and the Seidman Cancer Center of University Hospitals of Case Western University will occur as per Case Comprehensive Cancer Center standard operating procedures for monitoring of investigator initiated trials QA-8.1.0.

12.3.1 Investigator Responsibilities

Investigator responsibilities are set out in the ICH guideline for Good Clinical Practice (GCP) and in the US Code of Federal Regulations.

Investigators must enter study data onto CRFs or other data collection system. The Investigator will permit study-related audits by Novartis and Millennium or its representatives, IRB/EC review, and regulatory inspection(s) (e.g., FDA, EMEA, TPP), providing direct access to the facilities where the study took place, to source documents, to CRFs, and to all other study documents.

The Investigator, or a designated member of the Investigator's staff, must be available at some time during audits to review data and resolve any queries and to allow direct access to the subject's records (e.g., medical records, office charts, hospital charts, and study related charts) for source data verification. The data collection must be completed prior to each visit and be made available to the Novartis and Millennium so that the accuracy and completeness may be checked.

13 Statistical methods

13.1 Datasets to be Analyzed

13.1.1 Primary objectives and endpoints

13.1.1.1 Dose limiting toxicity

This study will use a 3 + 3 design (see under 5) to estimate whether select doses of MLN9708 up to a maximal target dose, chosen based on available data from other studies, are tolerated when combined with fixed doses of panobinostat and dexamethasone. Tolerance will be based on the ratio of patients developing dose limiting toxicity (DLT). Dose increase is allowed if 0 or 3 patients or 1 of 6 patients develop DLTs, while confirmation of a given dose level as tolerated requires treatment of at least 6 patients with no more than one patient developing a DLT.

Dose limiting toxicity (DLT) will be assessed during the first cycle and be defined as the following drug-related adverse events according to CTCAE version 4.03 (if an adverse event is attributed to progressive disease, it will not be counted as DLT):

- Grade 4 or higher neutropenia or thrombocytopenia that does not resolve to grade 3 or lower within 7 days after detection while MLN9708 (ixazomib) and panobinostat are held.
- QTcF increase to ≥ 480 msec that persists ≥ 7 days after withholding panobinostat and MLN9708
- Any grade 3 or higher non-hematologic adverse events except:
 - Nausea, vomiting, diarrhea, or electrolyte abnormalities that can be reduced to grade 2 with supportive measures within 7 days

Patients who cannot be assessed for DLT due to progressive disease or other reasons will be replaced.

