Phase II extension: Patients in phase I (median age 65, range 50-73, median previous regimens 5, range 2-10) tolerated treatment without DLT and without non-hematologic severe (grade 3 or higher) adverse event according to CTCAE vs.4.03. Three patients developed grade 3 hematologic toxicities (2 neutropenia, 1 thrombocytopenia). Worst diarrhea was grade 1 (n=6), worst nausea grade 2 (n=1) and 4 additional patients developed transient grade 1 nausea. Other possibly panobinostat or ixazomib related grade 1/2 adverse events included thrombocytopenia (n=5), neutropenia (n=3), fatigue (n=2), anemia (n=2), anorexia (n=1) and arthralgia (n=1).

Median QTcF before treatment start was 405 msec (range 378-430) and increased on average by 4.3% (maximally by 13%). One patient developed transient grade 1 QTcF prolongation to 552 msec. No other cardiac adverse events were observed. Of the 11 patients in phase I, one reached PR, two reached MR, and one had stable disease for 6 months. All patients entered the study with disease refractory to their last regimen, and in two of the responding patients (1PR, 1MR) this included a proteasome inhibitor an IMiD, and a glucocorticosteroid (carfilzomib, pomalidomide, dexamethasone in the MR patient, bortezomib, dexamethasone, lenalidomide in the MR patient). Overall, we are encouraged by activity in extensively pretreated patients and by excellent tolerance of this regimen so far. In phase II we aim to extend the study cohort by an additional 20 patients who will be treated until progression or other reasons for discontinuation arise (7.6.1) to strengthen the safety analysis and obtain a more reliable estimate of activity.

3 Study objectives

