3.2 Secondary Objective

- Assess response and clinical benefit response rates according to international uniform response criteria and adapted EBMT criteria, respectively (see under 8.1)
- Assess progression-free survival (PFS) and overall survival (OS)

4 Study endpoints:

4.1 Primary endpoints:

- Dose limiting toxicity (phase I) and tolerance according to CTCAE vs. 4.03 (phase I and II)

4.2 Secondary endpoints:

- Response to panobinostat, dexamethasone, ixazomib (MLN9708) will be assessed according to international uniform response criteria and clinical benefit response according to modified EBMT response criteria, comparing myeloma panels obtained at the beginning of each cycle that include SPEP, 24 h UPEP, serum and urine IFEs, and serum free light chains to results at screening. In addition a baseline bone marrow exam and skeletal survey will be obtained and repeated as clinically indicated and for assessment of complete remission (bone marrow).
- Progression-free survival will be measured from study entry to progression or death of any cause, whichever comes first.

- Overall survival for all will be measured from study entry to death from any cause.

5 Overall study design, treatment cycles, and study duration

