5.1 Study design and treatment cycles

Phase I: This study will use a modified 3 + 3 design to define the tolerability and safety of MLN9708 (ixazomib) administered to at least 6 patients with relapsed or refractory myeloma on a day 1,8,15 every 28 day schedule at up to 4mg in combination with fixed doses of panobinostat and dexamethasone.

Dose limiting toxicities (DLTs, see under 5.4) will be assessed at the end of the first cycle, on day 28. The trial will accrue up to three patients at any given DL who will need to be assessed for DLTs before the next three patients can be enrolled. Determination of the highest tolerated dose of two tested dose levels will require treatment of at least 6 patients at the respective dose level with no more than one patient developing a DLT.

The first three patients will be treated at DL1. If no patient develops any DLT, the next three patients will be enrolled at DL2. If 1 patient develops any DLT, three additional patients will be enrolled at DL1. If no more than 1 of 6 patients treated at DL1 develops a DLT, the next three patients will be enrolled at DL2. If 2 or more of 2-6 patients treated at DL1 develop DLTs further enrollment will be stopped and a change in the protocol will be discussed. If DL2 opens to enrollment, and 0-1 of the first three patients develop any DLT, additional three patients will be enrolled at DL2 and if no more than 1 of 6 patients treated at DL2 develop any DLT, DL2 will be considered a tolerated MLN9708 dose and further dose escalation will not be done. If 2 of three or up to 6 patients enrolled at DL2 develop any DLT, further enrollment at that dose level will be stopped and enrollment will continue at DL1 unless 6 patients have already been treated at that dose level. If no more than 1 patient treated at DL1 develops any DLT that dose level will be considered tolerated and an intermediate dose level may be discussed. If 2 or more of up to 6 patients treated at DL1 develop a DLT, further enrollment will be stopped and a change in the protocol will be discussed.

Phase II: Twenty additional patients will be treated at target doses of DL2 which has been found to be well tolerated without any DLT in phase I.

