5.4 Dose limiting toxicity

Dose limiting toxicity (DLT) will be assessed during the first cycle and be defined as the following drug-related adverse events according to CTCAE version 4.03 (if an adverse event is attributed to progressive disease, it will not be counted as DLT):

- Grade 4 or higher neutropenia or thrombocytopenia that does not resolve to grade 3 or lower within 7 days after detection while MLN9708 (ixazomib) and panobinostat are held.
- Use of G-CSF or platelet transfusions in cycle one
- Neutropenic fever (with grade 3 or grade 4 neutropenia)
- QTcF increase to ≥ 480 msec that persists ≥ 7 days after withholding panobinostat and MLN9708
- Any grade 3 or higher non-hematologic adverse events except:
 - Nausea, vomiting, diarrhea, or electrolyte abnormalities that can be reduced to grade 2 with supportive measures within 7 days

Patients who cannot be assessed for DLT due to progressive disease or other reasons will be replaced. Patients who develop a DLT may remain on study.

6 Study population

Patients with relapsed or refractory myeloma after at least two previous regimens including a proteasome inhibitor and an IMiD™ seen at the Cleveland Clinic Taussig Cancer Center will be screened for enrollment. Approximately 700 patients with multiple myeloma are seen each year at this site and approximately 600 have relapsed or refractory myeloma. The study will be offered to our partner institution within the Case Comprehensive Cancer Center, the Seidman Cancer Center of University Hospitals and Case Western University, where approximately 100 patients with relapsed or refractory multiple myeloma are seen each year. Participation is expected and would not alter per patient costs. We have accrued 11 patients to phase I in about 12 months and expect to enroll to phase II at a faster pace since no interruptions for DLT assessments will be required. We anticipate it will take about 18 months to accrue additional 20 patients to phase II. .

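### Section 13.1.1.1 restates the DLT definition with three of the five criteria in Section 5.4, so a phase I count made from it could fall short

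*Combined protocol and SAP*

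**What the plan says.** Section 4.1 makes DLT the phase I primary endpoint. Section 5.1, like the protocol summary, places the definition elsewhere: "Dose limiting toxicities (DLTs, see under 5.4) will be assessed at the end of the first cycle, on day 28".

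Section 5.4 gives five criteria. Two of them are "Use of G-CSF or platelet transfusions in cycle one" and "Neutropenic fever (with grade 3 or grade 4 neutropenia"). The other three concern unresolved grade 4 cytopenia, persistent QTcF prolongation, and grade 3 or higher non-hematologic events with stated exceptions.

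Section 13.1.1.1 says that tolerance rests on the proportion of patients with a DLT. It then says DLT will "be defined as the following drug-related adverse events according to CTCAE version 4.03" and lists only those other three. It refers to Section 5 for the 3 + 3 design, but it does not refer to Section 5.4 for the definition.

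Section 2 reports that phase I patients "tolerated treatment without DLT and without non-hematologic severe (grade 3 or higher) adverse event". It does not say which list was applied.

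**The concern.** Both sections are current text, and each reads as a complete definition. An analyst preparing the phase I report would naturally take the endpoint from the statistical section, and that section has the shorter list. A patient whose only qualifying event was cycle 1 G-CSF or a platelet transfusion, or neutropenic fever, is a DLT under Section 5.4. On the wording of Section 13 the same patient is not. What is at stake is whether the reported phase I primary endpoint follows the definition to which the design text points.

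**Working it through.** The plan gives no error rate, power or sample size formula for the DLT endpoint, so there is no figure to reproduce. The check compares the two lists and then the counts they produce.

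**Step 1. The lists side by side.**

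| Criterion | Section 5.4 | Section 13.1.1.1 |
|---|---|---|
| A. Grade 4 or higher neutropenia or thrombocytopenia, not resolved within 7 days with both drugs held | yes | yes |
| B. G-CSF or platelet transfusion in cycle 1 | yes | no |
| C. Neutropenic fever with grade 3 or 4 neutropenia | yes | no |
| D. QTcF of 480 msec or more, persisting at least 7 days off drug | yes | yes |
| E. Grade 3 or higher non-hematologic event, same exceptions | yes | yes |

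The cycle 1 window, the exclusion of events attributed to progression, and the replacement of patients who cannot be assessed are the same in both sections. The difference is B and C.

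**Step 2. Direction.** Each patient either has or lacks each of the five criteria, which gives 2^5 = 32 patterns.

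- DLT under 5.4 (any of five): 32 − 1 = 31 patterns.
- DLT under 13.1.1.1 (any of A, D, E): (2^3 − 1) × 2^2 = 28 patterns.
- DLT under 5.4 only: 31 − 28 = 3 patterns (B alone, C alone, B with C).
- DLT under 13.1.1.1 only: 0 patterns.
- Same answer under both: 28 + 1 = 29 patterns.

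For a fixed set of patients, the Section 13 count is therefore never above the 5.4 count. These are counts of patterns and not probabilities. The statement does not cover the possibility that the two lists would have led the 3 + 3 rule to enrol different patients.

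**Step 3. What this means for the reported zero.**

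- If 5.4 was applied, zero under five criteria implies zero under three, and the lists agree.
- If 13.1.1.1 was applied, zero under three leaves B and C unchecked.

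Section 2 mentions no neutropenic fever, so nothing reported points to C. Cycle 1 use of G-CSF or platelets is not reported either way, so B is the open route. Section 2 describes grade 3 hematologic toxicity in three patients (two neutropenia, one thrombocytopenia) and gives no timing. Section 7.4 allows G-CSF to reach the neutrophil threshold for starting cycle 2, and Section 7.7 allows it for severe neutropenia. Section 7.7.1 allows platelet transfusion when clinically indicated. None of these provisions excludes cycle 1.

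**The case against.** The best answer is that this is an outdated duplicate list with no effect on the trial. The design text points to 5.4, so the zero count may well rest on all five criteria, and then the two sections agree. Phase I accrual is complete, the phase II dose is fixed, and no phase II decision uses DLT. The route through G-CSF is also narrow. Table 7-4 suggests growth factor for grade 4 or febrile neutropenia and places prophylactic use in the following cycle, and Section 2 mentions no grade 4 cytopenia. The likeliest candidates are the three patients with grade 3 events, and only if they were treated in cycle 1.

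Most of this stands, and it is why the point is minor. It does not close the route, because the provisions in Step 3 still permit cycle 1 use. That 5.4 governs is itself an inference from the cross-references. If it is rejected, the protocol has two competing definitions of its phase I primary endpoint, and that needs correcting just as much. Reading neutropenic fever as a grade 3 non-hematologic event would narrow the gap, but G-CSF and platelet use would remain uncovered.

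Two stronger readings go too far:

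- **That DLTs were missed, or that DL2 was wrongly declared tolerated.** No reported event meets either omitted criterion, and nothing shows that the shorter list was used.
- **That patients enrolled before Amendment 4 were judged on the shorter list.** A reader might infer this because the Summary of Changes places the two criteria under 5.4 at that amendment and names no change to Section 13. The documents give no enrolment dates and no date on which the amendment took effect, and cohort pauses make even accrual a poor assumption. The current Section 5.4 makes no exception by enrolment date. The log may explain how the lists diverged, but it does not support a number of affected patients.

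**Conclusion.** The mismatch is certain: five criteria against three, with any error towards an undercount. Its demonstrated effect on the phase I result is nil. What remains is that the statistical section gives an incomplete rule for the phase I primary endpoint, and that the basis of the zero count is not stated. The consequence is confined to the phase I report, and the severity is minor. This rests on reading 5.4 as the operative list and on comparing the lists for the same patients.

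**What to change.** - Replace the list in 13.1.1.1 with a reference to Section 5.4, so that only one definition exists.
- Before phase I is published, check existing cycle 1 records for G-CSF use, platelet transfusion and neutropenic fever in all 11 phase I patients, and confirm that the zero count holds under all five criteria.
- State in the report that the Section 5.4 list was applied. If the check finds a qualifying event, correct the count.

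The cost is one cross-reference and a record check for at most 11 patients. No new data collection or design change is needed.
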